Aim 3. Pilot test measures to assess treatment outcomes within patients who self-identify as Hispanic/Latino at a health care clinic in New York and estimate measurement parameters for future efficacy testing (means and standard deviations).

Aim 4. Measure level of acculturation and rates of bi-directional travel in this study population.

Aim 5. Generate an explanatory model of HIV infection among patients in this clinical context and explore how it may be used to guide HIV-related communication using infographics.

Study Design

To complete the study aims, a mixed methods study will be conducted. The components of this study include:

- 1) One design session with health care providers at CHP-NYP
- 2) A single group pretest/posttest study design will be used to pilot test the infographic intervention
- 3) In-depth interviews with two stakeholders
 - a. Patient participants who receive the intervention
 - c. Members of the clinical team at CHP-NYP

An initial design session will be conducted to learn how to adapt infographics that were designed in the DR to be useful and relevant in a clinical setting in New York City. Changes will be incorporated into the designs and then the intervention will take place over the subsequent 8 months. During the intervention, patient participants will receive information using the infographics during study visits, which will take place after their normal visits to CHP-NYP. Baseline data will be collected from patient participants at enrollment and at 3- and 6-month follow up visits. In-depth interviews will be completed with a selection of patient participants to develop an explanatory model of HIV infection and HIV-related communication using infographics. Individual interviews will also be conducted with additional members of the CHP-NYP clinical team to explore factors related to intervention implementation.

Statistical Procedures

1) Design session with health care providers (N ≤ 10)

The audio recording of the design session with health care providers will be transcribed and analyzed with conventional content analysis to extract key points and recommended changes to infographic designs (Aim 1).

2) Single group pretest-posttest study design (N = 30)

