Descriptive statistics (means, standard deviations) will be calculated for all participant demographics. Responses to open-ended questions in baseline and follow up questionnaires will be grouped according to meaning and then, needed changes in infographic design or clinical processes will be determined (Aim 2). Scores on the acculturation scale will be calculated according to published recommendations (Aim 4).^{36,37} Mean scores and standard deviations will be calculated for each additional scale included in the follow up assessments and the change in mean scores between baseline and follow-up assessments determined (Aim 3). To take into account sex as a biological variable (NOT-OD-15-102), mean scores between male and female participants will be compared. Cronbach's alpha will be used to compare the reliability of measures with reported values and to support the assertion that these tools can be used within this population. Data collected will also be used to estimate parameters for use in determining effect sizes, which will be corrected for the bias inherent in small samples,³⁸ and reported as relative risks for categorical outcomes and as Cohen's D for continuous outcomes which will enable a more precise power calculation for subsequent study phases (Aim 3).

3.a.) Individual interviews with patient study participants (N ≤ 25)

We will conduct semi-structured individual interviews using an iterative interview guide (see attached interview guide) developed following the recommendations of Kallio 2016 which includes 1) internal testing by the research team; 2) expert assessment by specialists outside the research team; and 3) field-testing with the potential study participants.³⁹ Depending on when saturation is reached, up to 30 in-depth interviews will be conducted with participants who are enrolled in the study.

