Study team members who will administer the intervention will have a training regarding how guide patient education with infographics using the adherence counseling format that is used at CHP-NYP and will review principal components of intervention fidelity, including how to maintain it.^{47,48} During the intervention period, after normal clinic visits, study team members will guide education using the laminated, paper-based set of infographics developed in preliminary studies. Infographics will be available in both English and in Spanish and will provide a visual representation of the pertinent information to be included in clinical conversations. Intervention fidelity will be verified by audio recording up to one-half of total intervention visits with patient permission as is detailed in the informed consent document. Members of the study team will listen to audio recordings to confirm the other team member is using infographics during visits as specified in the intervention training, that both study team members are using them in the same way, and that they are delivering the intervention consistently across visits. Study team members will complete a second training session after the baseline visits to revisit main points that need to be addressed while administering the intervention and address any concerns that arise during the initial intervention visits. Patient participants will be asked about study team members use of infographics during follow up assessments.

Participant eligibility will be verified by clinic staff through electronic health records during team huddles that take place in the mornings on study days. A list of eligible participants will be provided to the health care providers who are seeing patients that day. The provider will then assess potential participant interest using the attached recruitment script and refer those who are interested in participating to an on-site study team member. That team member will then further introduce the study and then if a participant is interested, complete the informed consent process.

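### Cohen's d and relative risks from one uncontrolled pre-post group of 30 cannot support the planned claim of a more precise later power calculation, and their time point, SD and comparison are not defined.

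*Combined protocol and SAP*

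**What the plan says.** The Study Design section of the combined protocol and SAP states: "A single group pretest/posttest study design will be used to pilot test the infographic intervention". Item 2 of Statistical Procedures gives N = 30, with no control group and no derivation of that number.

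Item 2 names two quantitative score comparisons. For the scales in the follow-up assessments, the plan will have "the change in mean scores between baseline and follow-up assessments determined". In addition, "mean scores between male and female participants will be compared". Effect sizes then follow: relative risks for categorical outcomes and Cohen's d for continuous ones, "corrected for the bias inherent in small samples", "which will enable a more precise power calculation for subsequent study phases". Aim 3 is narrower. It asks the pilot to "estimate measurement parameters for future efficacy testing (means and standard deviations").

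Four other places bear on what a change from baseline contains:

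- Study Design: the infographics are delivered at "study visits, which will take place after their normal visits to CHP-NYP".
- Infographic intervention: visits are set at baseline, 3 and 6 months because CD4 count and viral load can respond within three months of starting ART.
- Measures: CD4 count and viral load are the primary outcomes.
- Inclusion Criteria: new patients or patients with a detectable viral load may enter. Study population characteristics describes all participants as having a detectable viral load.

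**The concern.** A power calculation for an efficacy comparison needs a target difference between groups and a measure of variability. One group can supply the variability. It cannot supply the between-group difference, because change from baseline adds together any effect of the infographics and everything else that happens over six months. The protocol names some of that itself: ordinary clinic care at the same visits, and response to ART in anyone who starts it.

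The effect-size sentence goes beyond Aim 3's means and standard deviations and offers d and relative risk for power. If a later controlled trial took d as its target, favourable background change would leave it underpowered and unfavourable background change would make it too large. Separately, d and the relative risk cannot be reproduced from the text, because the follow-up, the SD and the comparison are all open.

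**Working it through.** **Plan's own figure.** N = 30 cannot be re-derived: no alpha, power, effect size, SD or precision target is stated. The values of d, r and background change below, and the later trial's design, are assumptions and are not in the documents.

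**1. Which contrast is available.** Of the two comparisons in item 2, male versus female does not bear on the intervention. That leaves baseline to follow-up, which has no comparator.

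**2. What the small-sample correction does.** The plan does not name the method. With the usual factor at 29 degrees of freedom, 1 − 3/(4 × 29 − 1) = 1 − 3/115 = 0.974, a 2.6% reduction. It rescales d; it neither removes background change nor narrows the uncertainty.

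**3. Precision at n = 30.** Assume full follow-up and an observed d of 0.5 on the SD of change. Then t = 0.5 × √30 = 2.739 on 29 df. The noncentrality parameters that put 2.739 at the 97.5th and 2.5th percentiles, divided by √30, give a 95% CI of 0.116 to 0.876. Read as a between-group target (two-sample t, two-sided 5%, 80% power), those limits correspond to about 1,170 and 22 per arm. This is sampling error alone. It bears on the precision claim, not on the missing comparator.

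**4. Effect of background change.** Same test, assumed true between-group d of 0.2, which needs 394 per arm:

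| Background change added (SD) | Pre-post d | n per arm planned | Power at true d = 0.2 |
|---|---|---|---|
| 0 | 0.2 | 394 | 80% |
| 0.1 | 0.3 | 176 | 46% |
| 0.2 | 0.4 | 100 | 29% |
| 0.3 | 0.5 | 64 | 20% |

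In the other direction, background change of −0.1 SD gives a pre-post d of 0.1 and about 1,571 per arm where 394 would do. The documents do not allow the actual size or sign to be known.

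**5. Which SD.** With equal visit SDs and baseline–follow-up correlation r, the SD of change is √(2(1 − r)) visit SDs. A mean change of 0.5 visit SD is d = 0.5 on the visit SD. On the SD of change it is 0.5/√(2(1 − r)):

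- r = 0.3: 0.42
- r = 0.5: 0.50
- r = 0.7: 0.65
- r = 0.8: 0.79

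The same data can therefore give d anywhere from 0.42 to 0.79 over this range of r.

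**6. Relative risk.** Take suppression to mean not detectable. If all 30 are detectable at baseline (the Study population characteristics wording) and x are suppressed at follow-up, the relative risk of suppression is (x/30)/(0/30), which is undefined. The relative risk of being detectable is (30 − x)/30, which cannot exceed 1 by design. Under the Inclusion Criteria wording the baseline proportion need not be zero, but it depends on the mix of entry routes.

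**7. What one group can supply.** At n = 30 the 95% CI for an SD runs from √(29/45.72) = 0.80 to √(29/16.05) = 1.34 times the estimate. A correlation of 0.7 has a 95% CI of 0.45 to 0.85 (Fisher z).

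**The case against.** The strongest reply is that this is a feasibility and usability pilot, that Aim 3 asks only for means and SDs, and that a single group is suitable for both. That stands: neither the design nor Aim 3's parameters are at fault. The reply does not cover the effect-size sentence, which says d and relative risk themselves will be reported and will serve power. No caveat appears elsewhere.

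Several stronger readings are tempting, and the documents do not support them:

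- A reader might infer that the plan presents the change as the infographic effect, or commits to d as a later trial's target. It does neither. A controlled next phase is also an inference from the reference to future efficacy testing.
- A reader might say the contrast is wholly undefined. Its direction can be inferred; the time point, the SD and the relative-risk comparison cannot.
- A reader might take a change analysis of CD4 count and viral load as stated. It is explicit only for the scales, although Measures includes both laboratory outcomes in the assessments.
- A reader might assert regression to the mean in viral load. That depends on whether the qualifying sample is also the baseline, or on correlation decaying over time. The documents do not say which sample is the baseline.
- A new patient is not necessarily starting ART, and the number who will is not given.
- The training text, "using the adherence counseling format that is used at CHP-NYP", describes how the study team delivers the infographics. It does not show that participants receive separate counselling. The case for concurrent care rests on study visits following normal appointments.

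**Conclusion.** The point holds in a limited form. Pre-post d and relative risk from this pilot mix any infographic effect with concurrent care and possible ART response, and the small-sample correction does not separate them. The claim of a more precise power calculation is also unsupported on sampling error alone: about 0.12 to 0.88 around an observed d of 0.5, assuming 30 complete pairs and the SD of change. The undefined time point, SD and relative-risk comparison are plain omissions, and under one of the two eligibility wordings a relative risk of suppression against baseline cannot be computed.

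No pilot result changes and no participant is affected. The power losses tabulated above are illustrations that rest on assumed effects and on a later controlled trial adopting d as its target, which the plan does not say. It should be fixed because following the sentence as written would feed a confounded and imprecise figure into planning, when better planning quantities come from the same data.

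**What to change.** Confine the change to the effect-size sentence in item 2 of Statistical Procedures and to Aim 3, with one reconciliation under Subjects:

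1. Replace the power-calculation claim with a statement that pre-post d and relative risk are descriptive, uncontrolled changes and will not be used as a between-group target effect. How a later trial sets its target difference can be left to that trial's protocol.
2. Report for planning, each with a 95% CI: the SD at each visit, the SD of within-person change, the baseline–follow-up correlation, and retention at 3 and 6 months.
3. State the follow-up time point and the SD used in d. Where eligibility fixes the baseline proportion, report categorical outcomes as paired proportions with CIs instead of a relative risk. For example, 12 of 30 suppressed would be 40%, exact 95% CI 23% to 59%.
4. Reconcile Inclusion Criteria with Study population characteristics on whether all participants have a detectable viral load.

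The cost is protocol wording and a few more summary columns from data already being collected; no new patients or procedures. The downside is that the pilot yields no headline effect size for planning, and the quantities that replace it have wide intervals at n = 30, as step 7 of the working shows.

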The guide includes open-ended questions and probes designed to generate an explanatory model of participants' experience living with HIV and communicating about it in a clinical setting.^{40,41} Recruitment for in-depth interviews will continue until we have reached data saturation, when no new information is gleaned from the most recent interviews.⁴² Analysis of transcripts from in-depth interviews (Aim 5) will be guided by a qualitative descriptive (QD) methodology and will include conventional QD content analysis methods such as inductive line-by-line latent coding. An iterative content analysis method will then be used to generate codes and extract meaning from each question.⁴³⁻⁴⁵ A coding guide will be developed by one member of the research team after initial review of a subset of transcripts. Other team members will then review and refine the coding guide. Then, two members of the research team will code each transcript and discrepancies will be resolved by discussion until consensus is achieved. Analyses will be conducted in Spanish then translated to English for final dissemination. NVivo will be used to support data management and Gioia's methodology to ensure rigor in qualitative research will be followed.⁴⁶

3.b.) Individual interviews with members of the clinic team (N ≤ 10)

Audio recordings of these interviews will also be transcribed and main points regarding changes to the study and clinical utility of infographics in this setting will be extracted.

Privacy and Data Security

Provide a description of how the confidentiality of study data will be ensured, addressing concerns or protections that specifically relate to the data storage elements identified above (e.g. hard copy, electronic, system, and/or endpoint)

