After completing informed consent, patient participants will complete a baseline assessment using REDcap on an encrypted tablet with the help of a study team member prior to intervention administration (Table 1). Patient participants will then receive the intervention during study visits, which will take place after participants' normally scheduled appointments at baseline, 3- and 6-month visits. They will complete a follow up assessment at their visits closest to 3- and 6-months following their baseline visit. Study team members will extract information from patient medical records (CD4 count, viral load, current ART etc.) at each data collection time point. Patient participants will receive reminder phone calls prior to each of their study visits using the attached reminder phone call script. Time intervals were selected as CD4 count and viral load may change as early as three months after ART initiation.⁴⁹⁻⁵¹ Study team members will time how long it takes to administer the intervention.

Following their six-month study visit, participants will be asked to participate in an in-depth interview. At the end of the study, additional members of the clinical team will be interviewed to assess feasibility of infographic use in this clinical setting.

Table 1. Summary of research activities

Date(s)	Study point	Participants	Activities
July 2019	Design Session	• Members of clinical team	• Two hour design session
September 2019	Study team member training	• Study team members	• Two-hour training on how to use infographics
September/October 2019	Enrollment	• Patients • Study team	• Health literacy assessment • Baseline assessment • Exposure to intervention • CD4 & viral load extracted
December 2019/January 2020	3-month visits	• Patients • Study team	• Exposure to intervention • Follow up assessment • CD4 & viral load extracted
March/April 2020	6-month visits	• Patients • Study team	• Exposure to intervention • Follow up assessment • CD4 & viral load extracted
March – May	In-depth interviews	• Patients	• Follow up assessment • CD4 & viral load extracted
April/May	In-depth interviews	• Members of the clinical team	• Individual interviews with team members

Measures

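### Do the two patient-interview maxima in section 3.a and the patient-interview row of Table 1 call for a change to the plan?

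*Combined protocol and SAP*

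**What the plan says.** **Interview numbers.** Statistical Procedures sets the patient cohort in section 2 as "Single group pretest-posttest study design (N = 30". Section 3.a is headed "Individual interviews with patient study participants (N ≤ 25", and its first paragraph permits "up to 30 in-depth interviews will be conducted with participants who are enrolled in the study", subject to saturation. The section then gives the stopping rule: "Recruitment for in-depth interviews will continue until we have reached data saturation". Study Design describes the interviewees as a subset of the patients, and the Infographic intervention section offers each patient one interview after the six-month visit.

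**Schedule.** Study Design states: "Baseline data will be collected from patient participants at enrollment and at 3- and 6-month follow up visits". The Infographic intervention section states: "They will complete a follow up assessment at their visits closest to 3- and 6-months following their baseline visit". It also has medical records extracted whenever data are collected, while Measures ties CD4 count and viral load to each study visit. The compensation paragraph counts three paid study visits and pays the interview separately.

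In Table 1, the patient-interview row (March – May) gives its activities as "Follow up assessment • CD4 & viral load extracted" and does not mention the interview. The next row, for the clinical team, does name its own activity: "Individual interviews with team members".

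**The concern.** Two different maxima for one activity, one directly above the other, look like a planning error. If saturation has not been reached at interview 25, the team cannot tell from the protocol whether a 26th is allowed. The larger number also equals the whole cohort, which sits awkwardly with interviewing only a subset.

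The Table 1 row could matter more, because it touches outcome data. Read literally, it adds a third follow-up assessment, taken only in patients who agree to be interviewed. Section 2 of Statistical Procedures defines the Aim 3 change as running from baseline to follow-up without naming the follow-up points. An extra assessment in a self-selected subset could then enter the means, standard deviations and effect sizes meant to inform the power calculation for later studies.

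**Working it through.** **1. The two caps**

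Inputs: 25 (3.a heading), 30 (3.a paragraph), 30 (cohort size, section 2). Neither cap comes from a formula, so there is no planned figure to reproduce.

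- Difference: 30 − 25 = 5 interviews.
- Share of the cohort: 25/30 = 83.3%; 30/30 = 100%.

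The figures cannot be reconciled as 25 people giving 30 interviews, because each patient is offered a single interview and no repeats are described. The contradiction stands.

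Its reach is as follows:

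- The cap binds only if saturation has not been reached by interview 25. At most 5 interviews are then in question.
- The interviews serve Aim 5 and are analysed by qualitative content analysis. A saturation design needs no sample-size calculation, and none is offered.
- The Aim 3 means, standard deviations and effect sizes come from the pretest-posttest cohort of 30, not from the number interviewed. Moving the cap from 25 to 30 changes none of them.

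**2. The Table 1 row**

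| Patient time point | Follow-up assessment: Table 1 | Follow-up assessment: text | CD4/viral load: Table 1 | CD4/viral load: text |
|---|---|---|---|---|
| Enrollment | no (baseline) | no (baseline) | yes | yes |
| 3 months | yes | yes | yes | yes |
| 6 months | yes | yes | yes | yes |
| Interview | yes | not scheduled | yes | unclear |
| Total | 3 | 2 | 4 | 3, or 4 if the interview counts as a data-collection point |

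The one clear mismatch is therefore a single follow-up assessment (3 − 2 = 1), together with the missing mention of the interview. The laboratory entry is not a firm mismatch, because the rule in the Infographic intervention section can be read to cover the interview.

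Nor does the row establish a later measurement. Its window (March – May) overlaps the 6-month window (March/April 2020), and no minimum gap between the six-month visit and the interview is given. The entries could simply restate the 6-month collection for patients who are also interviewed. They also match two of the three activities in the 6-month row, lacking only exposure to the intervention. That pattern fits a copying slip, but the documents do not settle which explanation holds.

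**3. Which time points the Aim 3 analysis uses**

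Study Design and the Infographic intervention section both point to enrollment, 3 months and 6 months. These are also the three visits that every patient is scheduled and paid to attend. An analyst working from the text would compute change at 3 and 6 months and would have no stated reason to pool in a reading taken from interviewees alone.

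**The case for a change.** The best case for acting is practical. Staff work from the schedule table more than from the prose. A row that directs an unscheduled assessment burdens participants, and a row that omits its own main activity is poor guidance. The Aim 3 sentence names no time points, and the remedy would cost one number and one table row. Damage in reading the table is an unlikely explanation, since the row has its date, study point, participants and activities, and its neighbours are intact.

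Most of this is fair as description: the inconsistency exists and nothing in the document removes it. The consequence is what falls short. The text never says that follow-up assessments happen only at 3 and 6 months, so the table adds to the text rather than breaching a prohibition. Deleting the row's entries would rest on a guess about how they got there, and would discard planned data if they were intended. If the extra assessment were carried out, the Aim 3 time points in the text would still stand. On the cap, the question of a 26th interview is administrative: saturation, not the cap, is the scientific criterion, and either limit leaves the qualitative analysis as described.

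**Conclusion.** Both discrepancies are confirmed, and both are editorial. The caps differ by 5 interviews in a qualitative component governed by saturation. The schedule differs by one listed assessment and one omitted activity name. No estimate, precision statement, power figure or decision rule moves under either reading.

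This rests on two assumptions. Analysts take the Aim 3 follow-up points from the Study Design and Infographic intervention sections, which agree with each other. The Table 1 row also stands in the source as it reads here; the finding on the caps does not depend on that, since it comes from running text. The two places could be aligned at any routine edit, but the statistical plan does not need to change.
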